## 2 TRIAL OBJECTIVES AND ENDPOINTS

### 2.1 Objectives

The objectives of the trial are to:

- Investigate the single-dose pharmacokinetics of FE 999049 administered as a subcutaneous abdominal injection in healthy Chinese women
- Investigate the safety and tolerability of a single dose of FE 999049 administered as a subcutaneous abdominal injection in healthy Chinese women

[figure not shown]
### 2.2 Endpoints

- Pharmacokinetics (AUC, AUCt, Cmax, tmax, CL/F, Vz/F, t1/2)
- Safety (ECG, vital signs, laboratory parameters, adverse events)
- Injection site reactions
- Presence of anti-FSH antibodies

### 3 INVESTIGATIONAL PLAN

#### 3.1 Overall Trial Design

##### 3.1.1 Trial Design Diagram

**Figure 1 Overall trial design: sequence and timing of trial events for each subject**

##### 3.1.2 Overall Design and Control Methods

This is an open-label, randomised parallel group trial investigating the pharmacokinetics of a single subcutaneous abdominal injection of FE 999049. There will be 3 dose panels with 8 healthy Chinese women in each dose panel.

After testing negative in pregnancy tests, the subjects will receive two subcutaneous administrations of a 1-month depot formulation of the GnRH agonist DECAPEPTYL Depot 3.75 mg to down-regulate endogenous release of FSH during the trial. The first DECAPEPTYL Depot administration will be given  $28\pm1$  days prior to the first dose of IMP. In women not receiving hormonal contraceptives, the first DECAPEPTYL Depot administration should take place in the time interval 7 days before to 3 days after the expected start of menstruation. In women discontinuing combined oral contraceptives, the first DECAPEPTYL Depot administration should take place after the subjects have discontinued the hormonal contraception and within 5 days of commencement of bleeding. A second administration will be given  $10\pm1$  days prior to the first IMP administration.

To verify low stable endogenous hormones, serum FSH will be measured at Day -3 and Day -1. If any of the measurements is  $>5$  mIU/mL, the subject will be excluded.

The doses to be administered are 12, 18, and 24  $\mu$ g at a concentration of 33.3  $\mu$ g/mL.

For each subject the treatment period is 10 days, and the total duration of the trial from screening to the last follow-up visit after treatment will not exceed 13 weeks.

### **3.1.3 Trial Schedule**

The first subject is expected to be enrolled in 2019 with a total duration of the trial of approximately 7 months. The end of the trial is defined as the last visit (Visit 14, Day 28) for the last subject.

### **3.2 Planned Number of Trial Sites and Subjects**

The trial will be conducted at a single site, including 24 healthy women receiving active treatment.

### **3.3 Interim Analysis**

No interim analysis is planned.

### **3.4 Data Monitoring Committee**

No Data Monitoring Committee will be established for this trial. During the trial, the internal Safety Management Team at the sponsor will evaluate safety data on a regular basis.

## **3.5 Discussion of Overall Trial Design and Choice of Control Groups**

### **3.5.1 Trial Design**

Premenopausal women are chosen as trial population to mimic the target patient population. These women have endogenous biosynthesis and release of gonadotropin hormones. In order to minimise the interference of the endogenous FSH with the PK assessment of FE 999049, the GnRH agonist DECAPEPTYL Depot will be administered throughout the trial.

Subcutaneous injection has been selected as the route of administration for the trial since this is the intended route of administration in the clinical setting. The duration of the treatment period is governed by the expected half-life of FE 999049, which after a single subcutaneous administration is reported to be 40-44 hours. Thus, more than five half-lives, which is generally considered to be sufficient for a drug to be regarded as eliminated, are likely to have elapsed at the follow-up visit.

### **3.5.2 Selection of Endpoints**

The selected endpoints focus on evaluating the PK, safety, and tolerability of FE 999049 in Chinese women.

### **3.5.3 Blinding**

This is an open-label trial.

### **3.5.4 Selection of Doses in the Trial**

The selection of doses is governed by the anticipated doses that may be considered in the clinical setting. The trial will include 3 dose groups of 12, 18, and 24 µg FE 999049. The doses will enable the single dose PK determination of FE 999049 at each dose level and investigate dose proportionality in Chinese women. The lowest dose of 12 µg FE 999049 will be the daily administered dose in any phase 3 trial for IVF patients with an AMH level < 15 pmol/L. The 18 and 24 µg FE 999049 are the doses applied in a phase 3 safety trial in patients that require a higher FE 999049 dose in their second or third treatment cycle. The 24 µg dose will be the highest dose of FE 999049 applied for controlled ovarian stimulation (COS) prior to ART.

### **3.5.5 Selection and Timing of Dose for Each Subject**

All subjects will be dosed in the morning not less than 2 hours subsequent to a light standardised breakfast. This is assumed to minimise the possible analysis interference and variance caused by the intake of food just prior to sampling.

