**Table 1 Trial flow chart**

Visit No. Day	Screening	Run-in period				Treatment and Assessments								Follow-up	Anti-FSH ab		
		Ambulatory visits				Residential stay				Ambulatory visits							
	1	2	3	4	5	6	7	8	9	10	11	12	13	14			
-63 to -29	-28	-10	-3	-1	1	2	3	4	5	6	7	8	9	10	11	28	
Inclusion/exclusion criteria	X				X												
Informed Consent	X																
Randomisation					X												
Demographics	X																
Physical examination	X															X	
Medical history	X																
Gynaecological exam. and transvaginal ultrasound	X			X a	X a											X	
Cytology	X b															X	
Serum pregnancy test	X				X											X	
Urine pregnancy test		X c	X c														
FSH for eligibility determination (local laboratory)				X	X												
Blood sampling for PK determination						X d	X d	X d	X	X	X	X	X	X			
Urine drugs screen	X				X												
Alcohol breath test	X				X												
Serology	X																
Vital signs e	X			X	X f	X f	X f									X	
12-lead ECG	X			X	X f	X f	X f									X	
Clinical chemistry, haematology, and urinalysis	X			X				X								X	
Injection site reactions					X g												
Blood sampling for anti-FSH antibody analysis					X h						X					X	
Adverse events	X	X	X	X	X	X	X	X	X	X	X	X	X	X	X	X	
Prior/concomitant medication	X	X	X	X	X	X	X	X	X	X	X	X	X	X	X	X	
Administration of DECAPEPTYL Depot 3.75 mg		X	X														
Administration of IMP					X												

ab: antibody; ECG: electrocardiogram; FSH: follicle-stimulating hormone; IMP: investigational medicinal product; PK: pharmacokinetic;

a) Between Day -3 and Day -1

b) Cytology will be performed at screening if not done within 6 months prior to screening

c) Before the Day -28±1 and Day -10±1 DECAPEPTYL Depot administration

d) -1, -0.5, 0, 4, 8, 12, 16, 20, 24, 28, 32, 36, 40, 48 hours post-dose

e) Vital signs include systemic blood pressures, heart rate and body temperature

f) 12, 24 and 48 hours post-dose

g) Immediately, and 30 min and 24 hours after administration

h) Before administration of FE 999049

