### 7.1 Assessments Related to Endpoints

#### 7.1.1 Pharmacokinetics

Blood samples for measurement of serum concentration of FSH will be collected 1 and 0.5 hours prior to IMP administration, immediately before administration, and at 4, 8, 12, 16, 20, 24, 28, 32, 36, 40, and 48 hours, and 3, 4, 5, 6, 7, 8, and 9 days after administration. The actual sampling time at the ambulatory visits will be recorded. The serum concentrations of FSH will be analysed under the responsibility of the Department of Bioanalysis at Ferring Pharmaceuticals.

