9.1.1 Pharmacokinetic Endpoints

The calculation of PK parameters will be performed by Department of Translational Medicine, Ferring Pharmaceuticals. The PK parameters will be calculated for non-corrected as well as baseline corrected data by non-compartmental analysis (NCA) using the software Phoenix WinNonlin® (Certara, US). The baseline value is the mean of the three values obtained prior to the administration of the IMP (-1h, -30 min, 0 min). Baseline corrected values below LLQ will be set to zero. Actual sampling time points relative to dosing will be used for the NCA and on the individual plots of serum concentration versus time. Serum concentration values below lower limit of quantification (LLQ) and missing values (e.g. no blood sample collected or no value obtained at analysis) will be excluded from the estimation of λ_z . Values below LLQ will be represented as LLQ/2 in the plots and in descriptive statistics.

PK parameters will be estimated based on measurements from Day 1 to Day 10. From the serum concentration-time data of FE 999049 the following parameters will be estimated: AUC, AUC_t, % Extrap AUC, C_{max}, t_{max}, λ_z , t_{1/2}, CL/F, and V_z/F.

Selection of data points for calculation of t_{1/2} via λ_z will be based on the following considerations:

- The automatic range selection used in Phoenix WinNonlin® will be used to propose an optimal number of time points to use for the calculation of λ_z .
- The time range of samples used to estimate λ_z should preferably exceed the derived terminal half-life t_{1/2} ($= \ln 2/\lambda_z$).
- All the samples used to calculate λ_z should ideally fall in the log-linear terminal phase.
- At least three samples above LLQ obtained during the log-linear terminal phase will if possible be included in the calculation of the λ_z .

- The final selection of samples for calculation of λ_z will be based on visual inspection of log-concentration-time plots of individual profiles.

AUC will be calculated by the linear trapezoidal method. PK parameters will be summarised by treatment (i.e. dose group) using descriptive statistics.

Dose proportionality will be investigated for each of AUC and C_{max} using a multiplicative analysis of variance model (i.e. AUC and C_{max} will be log-transformed before analysis) with log(dose) as covariate. In this model, a covariate coefficient of 1 would indicate dose proportionality.

10 Safety

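### The 2-hour food gap in Protocol 3.5.5 runs to the dose, so at its minimum two of the three baseline samples fall only 1 h and 1.5 h after breakfast

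*Protocol*

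**What the plan says.** Protocol 3.5.5 sets the timing of the injection relative to food: "All subjects will be dosed in the morning not less than 2 hours subsequent to a light standardised breakfast". The only reason given is to "minimise the possible analysis interference and variance caused by the intake of food just prior to sampling".

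Protocol 7.1.1 then fixes the pre-dose sampling: "Blood samples for measurement of serum concentration of FSH will be collected 1 and 0.5 hours prior to IMP administration, immediately before administration". The next sample is at 4 h. Note d to Table 1 gives the same times.

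SAP 9.1.1 builds the baseline from these samples: "The baseline value is the mean of the three values obtained prior to the administration of the IMP". The non-compartmental analysis is run twice, once on non-corrected and once on baseline-corrected concentrations. Only the second uses this baseline.

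Neither document states a minimum interval from breakfast to a blood sample, and neither asks for the time of breakfast to be recorded.

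**The concern.** The rule and its reason have different end points. The reason concerns the interval from food to sampling; the rule controls the interval from food to dosing. The two coincide only for the sample drawn immediately before the injection. The other two pre-dose samples are taken earlier, and therefore closer to breakfast.

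The pre-dose samples are also the ones the rule is best placed to protect. The first post-dose sample comes at 4 h, so it is at least 6 h after that breakfast whatever the site does.

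What is at stake is the baseline-corrected set of PK parameters. A disturbance in a single post-dose sample affects one point on the curve. A disturbance in the baseline is subtracted from all of a subject's corrected values with the same sign. If food does affect the FSH measurement, as 3.5.5 allows for, the baseline is where the plan would least want it.

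**Working it through.** **Inputs**
- Breakfast to dose: at least 2 h (Protocol 3.5.5). I take this as counted from the end of the meal.
- Pre-dose sample times: -1, -0.5 and 0 h (Protocol 7.1.1; Table 1, note d; SAP 9.1.1).
- Weight of each sample in the baseline: 1/3 (SAP 9.1.1).
- Last PK sample: 9 days, or 9 × 24 = 216 h, after the dose (Protocol 7.1.1).
- Eligibility limit for FSH on Day -3 and Day -1: 5 IU/L (Protocol 3.5.6).
- Size of a food effect on measured FSH: not given.

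**Step 1: breakfast-to-sample gaps.** Gap = breakfast-to-dose interval + nominal sample time.

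| Breakfast to dose | -1 h sample | -0.5 h sample | 0 h sample | Samples under 2 h |
|---|---|---|---|---|
| 2 h (permitted minimum) | 1 h | 1.5 h | 2 h | 2 of 3 |
| 2.5 h | 1.5 h | 2 h | 2.5 h | 1 of 3 |
| 3 h | 2 h | 2.5 h | 3 h | none |

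For all three samples to be at least 2 h after food, the interval to the dose must be at least 2 + 1 = 3 h. At the 2 h minimum, the first post-dose sample is 2 + 4 = 6 h after breakfast.

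**Step 2: effect on the baseline.** If food shifts the two early readings by a fraction d and leaves the third alone, the baseline mean shifts by (d + d + 0)/3 = 2d/3. The values of d below are assumptions for illustration only.
- d = 1%: 0.67%
- d = 5%: 3.3%
- d = 10%: 6.7%

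**Step 3: upper bound on corrected area up to the last sample.** Shift in area ≤ (2d/3) × baseline × 216 h.

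| Assumed d | Baseline 1 IU/L | Baseline 5 IU/L |
|---|---|---|
| 1% | 0.007 IU/L; 1.4 IU·h/L | 0.033 IU/L; 7.2 IU·h/L |
| 5% | 0.033 IU/L; 7.2 IU·h/L | 0.167 IU/L; 36 IU·h/L |
| 10% | 0.067 IU/L; 14.4 IU·h/L | 0.333 IU/L; 72 IU·h/L |

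These areas are ceilings. They assume that no post-dose sample is affected by food and that the error carries through all 216 h. In practice AUC_t stops at the last quantifiable value, and SAP 9.1.1 sets corrected values below the quantification limit to zero. The 5 IU/L row is only a guide, because eligibility is checked at a local laboratory on other days. The effect on λz and on the extrapolated part of AUC was not computed.

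**The case against.** The strongest reply is that nothing in the plan is violated. Section 3.5.5 requires 2 h from breakfast to dose, and a site that does this complies. Neither document defines how close to sampling is too close, and the meal is light and standardised. Two hours is also a floor, and a site that serves breakfast 3 h before dosing has no shortfall. All of this stands. It limits the point to a rule that may miss its purpose; it does not explain why the interval ends at the dose when its reason concerns sampling.

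A second reply is that the effect may be nil. The protocol calls the interference only possible and gives no figure. This also stands.

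Three stronger readings are tempting, and the documents do not support them.
- A reader might infer that every reported concentration is affected. The non-corrected analysis subtracts nothing, and concentrations are reported both ways.
- A reader might infer a distorted dose-proportionality slope. With no food effect stated, any slope figure would rest entirely on an invented input. The plan also does not say whether the slope uses corrected or non-corrected data.
- A reader might infer that the morning samples on Days 4 to 10 need a meal rule because neither document gives one. Sampling procedures are delegated to a laboratory manual (Protocol 7 and 7.3) that is not among the documents, so its absence here proves nothing. If those samples also followed a meal, part of any interference would cancel on subtraction.

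**Conclusion.** The point holds as a minor design improvement. The mismatch between the rule and its reason is certain from the text: at the permitted minimum, two of the three samples averaged into the baseline are 1 h and 1.5 h after food, and only one reaches 2 h. Whether this matters numerically cannot be established. It depends on breakfast ending less than 3 h before the dose and on food affecting the FSH assay at all. If food has no such effect, the change gains nothing.

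It would be wrong to report this as a breach of the protocol's own condition. The sponsor judged food interference worth a rule, and the rule as worded does not fully cover the samples it can most usefully protect. Only the baseline-corrected results are exposed.

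**What to change.** Reconcile Protocol 3.5.5 with 7.1.1: count the existing 2-hour interval from the end of breakfast to the first pre-dose PK sample (-1 h) instead of to the dose, and record the time of breakfast on Day 1.

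The cost is a breakfast up to about one hour earlier on Day 1, when subjects are already resident in the clinic, plus one recorded time and a sentence or two of text. No sample, visit or dose amount changes.

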### **3.5.6 Withdrawal Criteria**

In order to ensure down-regulation and minimise any interference from endogenous FSH, any subject that does not have a FSH concentration  $\leq 5$  IU/L on Day -3 and Day -1 will be withdrawn from the trial before randomisation. The Day -3 assessment may be repeated up to 5 days later if the first FSH measurement is  $> 5$  IU/L (subsequent visits will be postponed accordingly). The second assessment and the Day -1 assessment must be within acceptable ranges. No other specific withdrawal criteria are defined.

Since this trial comprises a single subcutaneous injection, no specific withdrawal criteria are defined that will arrest the treatment.

## 4 SELECTION OF TRIAL POPULATION

### 4.1 Trial Population

Healthy Chinese women, 21-40 years of age and with a body mass index (BMI) of 18.5-25 kg/m^2, with a normal menstrual cycle, may be included in this trial.

#### 4.1.1 Inclusion Criteria

All of the following inclusion criteria must be met before the subject can enter into the trial:

1. Signed written Informed Consent Form
2. Female of Chinese origin, with two ethnic Chinese parents and four ethnic Chinese grandparents
3. 21-40 years of age (both inclusive)
4. Willing to stop using combined oral contraceptives (COC) in relation to the first DECAPEPTYL Depot administration on Day -28
5. Agrees to use a double barrier method of contraception between Day -63 and Day 28, if not abstinent. A double barrier method of contraception should also be used after Day 28 until menses resumes or until another contraceptive method has been established
6. Normal menstrual cycles with a range of 24-35 days in the absence of oral contraceptives
7. Serum follicle-stimulating hormone (FSH) ≤5 IU/L on Day -3 and Day -1
8. Body mass index (BMI) of 18.5 -25 kg/m^2 (both inclusive)
9. Negative serology for human immunodeficiency virus (HIV) antibody, hepatitis B (surface antigen), hepatitis C antibody, and syphilis bacteria
10. Healthy according to medical history, physical examination, gynaecological examination, electrocardiogram (ECG), blood pressure, and laboratory profile of blood and urine
11. Negative urine drug screen and alcohol breath test at screening and on Day -1
12. Non-smoker or light smoker (≤5 cigarettes/day) for at least 6 months prior to trial start

#### 4.1.2 Exclusion Criteria

Any subject meeting one or more of the following exclusion criteria cannot be included in the trial and will be withdrawn if occurring during the trial:

1. Presence or a history of clinically significant diseases of the renal, hepatic, gastrointestinal, cardiovascular, or musculoskeletal systems, or presence or history of clinically significant reproductive, psychiatric, immunological, endocrine or metabolic diseases
2. Cancer within the last 5 years except for adequately managed basal cell carcinoma and squamous cell carcinoma of the skin
3. Pregnancy or breastfeeding

4. Current or a history of endocrine abnormalities such as hyperprolactinaemia, polycystic ovary syndrome or other ovarian dysfunction, tumours of the pituitary gland or hypothalamus, thyroid or adrenal disease
5. Clinically significant findings on the trans-vaginal ultrasound, cytology, gynaecological or breast examination at screening or on Day –1 including ovarian cysts or tumours of the ovaries or uterus
6. Contraindications for the use of gonadotropins and gonadotropin-releasing hormone (GnRH) agonists
7. Previously treated with gonadotropins within the last 6 months prior to screening
8. History within the last two years or current abuse of alcohol or drugs
9. Presence or history of severe allergy or anaphylactic reactions
10. Intake of prescribed medication, over-the-counter (OTC) medication, or herbal medicines, with the exceptions of COC, cromoglycate, and paracetamol according to the labelling, within 2 weeks or 5 half-lives of the drug, whichever is longer, prior to first dose of DECAPEPTYL Depot. Topical treatments of bacterial or fungal infection are allowed if stopped before first dose of IMP.
11. Intake of any non-registered investigational drug within the last 12 weeks preceding screening, or longer if judged by the investigator to possibly influence the outcome of the current trial
12. High daily consumption of caffeine-containing beverages (e.g. more than five cups of coffee or equivalent) with a risk of withdrawal symptoms arising during the trial that may confound the safety evaluation
13. Blood donation or major blood loss ( $\geq 500$  mL) within the last 8 weeks, or plasma donation with the last 4 weeks preceding the first day of IMP dosing
14. Current non-smokers or light smoker with a history of long-term, heavy smoking ( $>10$  pack-years)
15. Previously dosed in this trial
16. Mental incapacity or language barrier precluding adequate understanding or co-operation
17. Considered by the investigator to be unsuitable to participate in the trial for any other reason

## **4.2 Method of Assigning Subjects to Treatment Groups**

### **4.2.1 Recruitment**

The subjects will be recruited from the healthy subject database of the clinical site conducting the trial, and by advertising.

#### **4.2.2 Randomisation**

The subjects will be randomised into three dose groups (12, 18, and 24 µg) according to a computer-generated randomisation list provided by Global Biometrics, Ferring Pharmaceuticals. Randomisation will be carried out in the morning of the administration day. In case a withdrawn subject is replaced, she will receive the same dose as the subject she is replacing.

### **4.3 Restrictions**

#### **4.3.1 Prior and Concomitant Therapies**

No concomitant medication, including Chinese herbs, is allowed, except for treatment of AEs when necessary, cromoglycate, and paracetamol according to label. Combined oral contraceptives should be stopped prior to first dose of DECAPEPTYL Depot; this will be administered on Day -28 and within 5 days of commencement of bleeding, and may not be used during the trial. Topical treatment of bacterial or fungal infection is allowed if stopped before IMP administration. Any concomitant medication will be recorded in the electronic case report form (e-CRF), together with the main reason for its prescription. Also the dose and dosage regimen will be documented in the e-CRF.

#### **4.3.2 Other Restrictions**

Subjects should abstain from drinking alcoholic beverages for 72 hours before the screening and all subsequent visits to the clinical investigation unit. In addition, subjects should abstain from drinking coffee and alcoholic beverages during the residential session in the treatment period.

Intake of products containing poppy seeds (e.g. poppy cake) should be avoided for a period of at least 48 hours before screening and admission to the clinic in order to avoid analytical interference with the drug screen for opiates.

The subjects should abstain from strenuous physical activity that is not within the subject's normal weekly routine for 48 hours prior to screening, and from 48 hours prior to admission until the last safety examination.

